Telephone counseling is an evidence-based treatment modality for smokers with SMI. Telephone counseling has broad reach and is inexpensive per user. Quitlines are available nationwide and cost ~\$1.69 per caller. Quitline counseling can help smokers with psychiatric diagnoses to quit, for example, 16% of Quitline callers with a psychiatric diagnosis were abstinent at 7 months post enrollment. However, quit rates for callers with psychiatric diagnoses were 20% lower than those without. Telephone counseling outcomes are improved with: mental health tailoring, when combined with care coordination with providers, or in-person group counseling. In one study, mental health tailored telephone counseling was as effective as face-to-face counseling and better attended. With sufficient dose and mental health tailoring, telephone cessation counseling is highly effective. Telephone counseling and care coordination could be added to brief provider interventions to provide patients with the intensity of treatment needed for smokers with SMI.

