## **3.5 Inclusion and Exclusion Criteria**

### **3.5.1 Inclusion Criteria**

Inclusion criteria for patients: daily cigarettes smokers (smoking >25 days/month), English speaking, patient in one of the two community mental health center study sites. Inclusion criteria for providers/staff: must be staff member at one of the community mental health center study sites.

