## 6.2 Efficacy Evaluations

Feasibility will be measured by the percent of providers who: attend the online and in person trainings, complete role plays, attend coaching calls, and receive performance feedback. We expect the majority (>75%) of providers and leaders to attend the trainings and receive performance feedback. For patients, feasibility will be measured by the proportion of patients who enroll in the study, the proportion who accept a proactive outreach and the proportion who complete the follow-up. Previous studies (preliminary studies 1-3) using this recruitment strategy have yielded a 30-44% response rate to the enrollment invitations, 62-71% for the proactive call, and 66-74% for follow-up assessment. Results in this range would be considered feasible.

Acceptability. Patients will complete the 8-item Client Satisfaction Questionnaire (CSQ) during the follow-up assessment. Qualitative interviews with 5-6 patients and 5-6 providers will be conducted at the 3-month follow-up (study 2), and 15 month follow-up (study 3). Interviews will be conducted by a trained research staff member. Interviews will contain open ended questions about treatment (for patients) and implementation (for providers and leaders) acceptability, burden, and suggestions for improvement.

Effectiveness. Implementation Effectiveness will be evaluated by the proportion of patients who receive the 5As and the proportion who report using smoking cessation counseling and medication measured 3-months after the start of the implementation period (study 2) and at 3, 6, and 12 months post baseline 2 (study 3) assessed via patient report. Patient Effectiveness will be measured by carbon monoxide (CO)-confirmed 7-day point-prevalence from tobacco post-intervention (3 months for study 2 and 12 months from second baseline for study 3). Secondary patient outcomes will include: 30-day point-prevalence abstinence, the number of self-reported ≥24 hour quit attempts and reductions in smoking via cigarettes per day.

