Acceptability will be assessed based on the 8 item Client Satisfaction Questionnaire (CSQ) during the follow-up assessment, as well as qualitative interviews at the 12-month follow-up. Interviews will contain open ended questions about treatment (for patients) and implementation (for providers and leaders) acceptability, burden, and suggestions for improvement. The treatment will be considered acceptable if  $\geq 80\%$  of participants respond that they are at least somewhat satisfied with their participation. Average acceptability scores will be reported. Initial effectiveness will be evaluated with respect to both implementation and patient outcomes. First, we will summarize CMHC-level implementation data with respect to treatment delivery and utilization (e.g., proportion of patients receiving each of the 5A's, using smoking cessation counseling and medication) and compare across centers. Next, baseline, 3-, 6-, and 12-month patient cessation outcomes (7-day PPA and number of quit attempts), will be summarized among the aggregate sample and by CMHC. We will explore the adjusted effects using a series of generalized linear mixed effects models adjusted for potential confounders, baseline values and clustering. Models allow for flexible distribution of the outcome (binary, count) and adjust standard errors for the clustered nature of the data (clustered by provider within CMHC). Models will include a random effect for CMHC and will further adjust for potential confounders (including variables that might differ between CMHC's). Similar models can be used to test the effects on secondary outcomes (e.g., cigarettes per day) during the post-implementation period (3-, 6- and 12-months) adjusting for baseline, and to explore the effect of implementation at the patient level (use of counseling and medication) and at the provider level (SSL dose) as a predictor of primary and secondary cessation outcomes.

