## 7.2 Sample Size and Power

Sample size considerations. The proposed sample size was estimated in order to have sufficient power to assess feasibility and acceptability as well as estimate initial effectiveness, within the confines of a pilot study. We propose to enroll 50 patients and 18-27 providers as part of the Aim 3 pilot study. With a two-sided alpha-level of 0.05, we will have more than sufficient power ( $>80\%$ ) to assess feasibility and accessibility and within-subjects effects in the small-medium range,  $f^2=.08$ .

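### With roughly 3 to 8 events expected, the planned adjusted mixed model is poorly suited to CO-confirmed 12-month abstinence in study 3; report an exact interval and use a penalised fit

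*Combined protocol and SAP*

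**What the plan says.** Section 6.2 defines patient effectiveness as "carbon monoxide (CO)-confirmed 7-day point-prevalence from tobacco post-intervention", taken in study 3 at 12 months from the second baseline. The study 3 procedures (headed 4.2.3) ask for a CO test only from patients who report abstinence at that 12-month visit.

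Section 7 first summarises 7-day abstinence and quit attempts at baseline, 3, 6 and 12 months, overall and by centre. It continues: "We will explore the adjusted effects using a series of generalized linear mixed effects models adjusted for potential confounders, baseline values and clustering". The models carry a random effect for CMHC and allow for clustering by provider. Counselling use, medication use and SSL dose are named as possible predictors of cessation. The section gives no list or number of covariates, no method for sparse events, and no fallback if a model does not converge.

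Other places that bear on this:

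- Section 7.2: "We propose to enroll 50 patients and 18-27 providers as part of the Aim 3 pilot study".
- Section 4.3.2 places study 3 at one of the two centres and study 2 at the other.
- Section 3.5.1 admits "daily cigarettes smokers (smoking >25 days/month".
- Section 6.2 treats "66-74% for follow-up assessment" as feasible.
- Section 2 cites the only absolute abstinence rate in the documents: "16% of Quitline callers with a psychiatric diagnosis were abstinent at 7 months post enrollment".

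**The concern.** A binary model draws its information from the rarer outcome. With a handful of abstinent patients and several covariates, maximum likelihood can separate, so that no finite estimate exists. When it does fit, it tends to overstate effects. The plan also asks for a centre variance from very few centres, and for adjustment for baseline values of an outcome that hardly varies at entry. At stake are the adjusted odds ratios for the named patient effectiveness outcome, which serves the initial-effectiveness part of Aim 3. The feasibility and acceptability aims are not touched.

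**Working it through.** **The plan's own figure.** Section 7.2 gives no expected number of abstinent patients. It claims, "With a two-sided alpha-level of 0.05", more than 80% power for "within-subjects effects in the small-medium range", f² = .08.

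- Regression reading: noncentrality 0.08 × 50 = 4, one tested predictor, power 0.50.
- Repeated-measures ANOVA reading: f = √0.08 = 0.283, and uncorrelated measures give power 0.79 (two measures), 0.87 (three) or 0.96 (five).

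The documents do not say which reading applies, so the claim is neither confirmed nor refuted. On either reading it says nothing about a binary abstinence model.

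**Expected events** = patients × follow-up × abstinence rate. Both rates are assumptions: 16% is borrowed from the background section, and 10% shows a lower case.

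| Analysed | At 16% | At 10% |
|---|---|---|
| 50 (all) | 50 × 0.16 = 8.0 | 5.0 |
| 37 (50 × 0.74) | 37 × 0.16 = 5.9 | 3.7 |
| 33 (50 × 0.66) | 33 × 0.16 = 5.3 | 3.3 |

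At 16%, the 90% binomial range is 4 to 12 events with 50 analysed and 2 to 9 with 33. With five covariates there would be 5.3/5 = 1.1 to 8/5 = 1.6 events per covariate.

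**Baseline term.** Smoking on more than 25 days means at least 26. That leaves at most 30 − 26 = 4 (or 31 − 26 = 5) smoke-free days in a month, fewer than 7. Abstinence at Baseline 1 is therefore essentially zero for everyone and cannot adjust anything. Baseline 2, about three months later, could vary a little.

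**Centre term.** Study 3 has one centre, so its centre variance cannot be estimated. Pooling with study 2's 25 patients gives two centres and 75 × 0.16 = 12 events, or 7.9 to 8.9 at 66-74% follow-up. Centre would then coincide with study, and study 2 measures CO at 3 months, not 12.

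**Ordinary logistic regression, simulated** (16% abstinence; 4 to 6 covariates, an assumed number; no random effects):

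| Analysed | Datasets with separation |
|---|---|
| 50 | about 1-13% |
| 37 | about 4-33% |
| 33 | about 5-41% |

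The width of these ranges comes mainly from covariate type. In one set of runs, all-continuous covariates gave 1-2% (n=50) and 4-14% (n=33); making two of them binary gave 8-9% and 24-30%. A separate simulation with five covariates (true odds ratio 2 for the predictor of interest, 1.5 for the others) gave 14%, 29% and 38% at n = 50, 37 and 33. At 10% abstinence it gave 38% at n=50 and 57% at n=37.

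Where the 4-to-6-covariate model fitted at 16% abstinence, the mean log odds ratio was about 1.3 to 1.9 times the truth and the median about 1.1 to 1.4 times. With 1 to 3 covariates there was little average inflation (0.8 to 1.1).

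**With a provider random intercept** (22 providers, SD 0.5, 3 or 5 covariates, n = 50 and 35):

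- 8-28% of datasets separated.
- Of the rest, about half put the provider variance at zero and 9-33% had runaway estimates.
- The mean log odds ratio was 1.5 to 1.9 times the truth.

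**Repeated self-report at 3, 6 and 12 months** (patient random intercept, assumed SD 2): 0-5% separated, 0-8% runaway, mean 0.8 to 1.2 times the truth.

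**Alternatives.** Exact 95% intervals: 5/33 is 5.1-31.9%; 6/37 is 6.2-32.0%; 8/50 is 7.2-29.1%. Firth fits converged in every run. The mean log odds ratio was 1.01 to 1.05 times the truth with five covariates (SD 0.95 to 1.14) and 0.98 to 1.05 times with two (SD 0.87 to 1.07).

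**The case against.** The models are labelled exploratory and follow a descriptive summary, so the plan already puts the proportion first. That stands, and it limits the weight of the point. But the plan attaches no interval to that proportion and names no method suited to few events.

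The plan does not fix the number of covariates. With one or two, and all 50 patients analysed at 16%, separation was only about 5-6%. That also stands: the size of the problem depends on a choice the plan leaves open.

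Section 7 names 7-day abstinence at several visits and does not confine the models to the CO-confirmed result. A repeated-measures model of self-report behaves far better. This is why the point is limited to the CO-confirmed outcome, which exists only at 12 months in study 3.

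Several stronger readings are tempting but unsupported:

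- A reader might infer that the model cannot be estimated or will usually fail. At n=50 most simulated datasets did not separate.
- A reader might take 16% as the trial's expected rate. It describes people who called a quitline, and these patients are approached proactively.
- A reader might infer that the plan commits to Baseline 1 abstinence as a covariate. Section 7 asks for baseline values in general and mentions baseline adjustment again for secondary outcomes such as cigarettes per day.
- A reader might infer that the odds ratio will set the next trial's assumptions. No section says so.

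**Conclusion.** The point holds for CO-confirmed 7-day abstinence at 12 months in study 3. About 5 to 6 events are expected at 66-74% follow-up and 8 if all 50 are analysed, assuming 16%; about 3 to 5 assuming 10%. The centre random effect has no basis with one centre and almost none with two, and a Baseline 1 abstinence term carries no information. Neither conclusion needs simulation. With 4 to 6 covariates, which is an assumption, separation is a minor risk to a substantial one depending on follow-up and covariate type, and average inflation of the log odds ratio is about 1.3 to 1.9 times. It does not follow that every abstinence model in section 7 is unsound: the repeated self-report models and those for cigarettes per day can stay.

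**What to change.** In section 7, add wording to this effect:

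> For study 3, CO-confirmed 7-day abstinence at 12 months is reported as a proportion with an exact (Clopper-Pearson) 95% interval; this is the main result for the outcome. Any adjusted model for it uses Firth-penalised logistic regression with one or two covariates named before the data are examined, no Baseline 1 abstinence term and no CMHC random effect. If studies 2 and 3 are pooled, site enters as a fixed term. Mixed models are retained for cigarettes per day and for repeated self-reported outcomes.

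The limit of one or two covariates is a matter of precision, since Firth fits with five also converged. Even with two covariates and n=50, an SD of 0.87 means a factor of about exp(1.96 × 0.87) = 5.5 either way: around a true odds ratio of 2, roughly 0.36 to 11.

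The cost is analysis-plan wording. What is lost is a fully adjusted model and a provider random effect for CO-confirmed abstinence, and with them a joint look at counselling, medication and SSL dose for this outcome. Estimates remain imprecise whichever method is used.

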## 7.1 Primary Endpoint

For study 2, the primary end point is 3 months post-implementation. For study 3, the primary end point is 12 months post-implementation (~15 months post-first baseline).

### 7.1.1 Safety Analysis

All subjects entered into the study at Visit 1 will be included in the safety analysis. The frequencies of AEs by type, body system, severity and relationship to study intervention will be summarized. SAEs (if any) will be described in detail. AE incidence will be summarized.

## 7.2 Sample Size and Power

Sample size considerations. The proposed sample size was estimated in order to have sufficient power to assess feasibility and acceptability as well as estimate initial effectiveness, within the confines of a pilot study. We propose to enroll 50 patients and 18-27 providers as part of the Aim 3 pilot study. With a two-sided alpha-level of 0.05, we will have more than sufficient power ( $>80\%$ ) to assess feasibility and accessibility and within-subjects effects in the small-medium range,  $f^2=.08$ .

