# 7 STATISTICAL CONSIDERATIONS

Qualitative analysis. Using a structured debriefing form, post-interviews notes will be written at the end of each interview and reviewed by all co-investigators. Interviews will be transcribed and deidentified. Transcription will be completed by Landmark Associates Inc. We will develop analytical codes using an iterative method in which interview notes are reviewed to: 1) consider whether the qualitative agenda is appropriate and complete, and 2) develop an initial coding structure. Deductive codes will be drawn from the interview questions (e.g., treatment needs); review of the interview notes will also allow the creation of inductive codes which capture emergent concepts from the interviews. Investigators and trained study staff will code the transcripts. Each transcript will be independently coded by two coders, who will meet to resolve discrepancies. Final codes will be entered into NVivo qualitative data analysis software. We will conduct a framework matrix analysis to identify the most effective ways to organize the content and logistics of implementation strategy and pilot study design and will help guide our pilot study protocol.

Quantitative Analysis. As a preliminary step, CMHC, provider, and patient-level characteristics will be summarized at baseline. Differences between CMHC's will be tested using graphical methods, non-parametric, and parametric tests as appropriate (e.g., Wilcoxon rank-sum test for skewed data, t-tests for normally distributed continuous data & chi-squared tests for categorical data). Consistent with Aim 3, feasibility and acceptability will be assessed as follows: feasibility will be measured by the percent of providers who attend the online and in person trainings, complete role plays, and receive performance feedback. Implementation will be considered feasible if at least 75% of providers and leaders attend the trainings and receive

performance feedback. For patients, feasibility will be measured by the proportion of patients who enroll in the study, the proportion who accept a proactive outreach and the proportion who complete the follow-up. The study will be considered feasible if results are in the range of those found in preliminary studies: 30-44% response rate to the enrollment invitations, 62-71% for the proactive call, and 66-74% for follow-up assessment (See Preliminary Studies Section).

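### Section 7.2 claims more than 80% power to assess feasibility and acceptability, but the plan sets no hypothesis for either, and the patient feasibility ranges do not say whether exceeding them counts as a pass

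*Combined protocol and SAP*

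**What the plan says.** Section 7.2 gives the purpose of the sample size: "The proposed sample size was estimated in order to have sufficient power to assess feasibility and acceptability as well as estimate initial effectiveness". It sets the numbers: "We propose to enroll 50 patients and 18-27 providers as part of the Aim 3 pilot study". It then claims more than 80% power, at two-sided alpha 0.05, "to assess feasibility and accessibility and within-subjects effects in the small-medium range", with f² = .08 attached to the within-subjects effects. The word accessibility there is evidently a slip for acceptability, the term in the section's opening sentence.

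The criteria are in Section 7:

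- Providers: "Implementation will be considered feasible if at least 75% of providers and leaders attend the trainings" and receive performance feedback.
- Patients: "The study will be considered feasible if results are in the range of those found in preliminary studies", namely "30-44% response rate to the enrollment invitations, 62-71% for the proactive call, and 66-74% for follow-up assessment".
- Acceptability: at least 80% of "participants respond that they are at least somewhat satisfied with their participation".

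Section 6.2 gives the same patient ranges and adds: "Results in this range would be considered feasible".

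**The concern.** Power and a two-sided alpha are properties of a test. For feasibility and acceptability the plan states no null rate, alternative rate, test or confidence-limit criterion, and the only effect size belongs to something else. Feasibility and acceptability are named questions of Aim 3, so the sample-size section promises a property on the main questions that the design does not have.

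The patient rule has a second problem. Its ranges have an upper end, and the text does not say what happens above it. Taken literally, a study that retained more patients than the preliminary studies would fall outside the range. If the reading is left open, the feasibility conclusion can depend on how the sentence is interpreted once the results are known.

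**Working it through.** **1. The plan's own figure.** The inputs in Section 7.2 are 50 patients, 18-27 providers, two-sided alpha 0.05 and power above 80%. For feasibility and acceptability the figure cannot be reproduced, because the null and alternative rates are missing. What can be computed is the chance that an observed proportion meets each cut-off at a given true rate p. That is a pass probability, not power.

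**2. Patient ranges read as a band.** Let X ~ Binomial(50, p), with one yes/no outcome per patient.

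- Outreach 62-71%: 0.62 × 50 = 31 and 0.71 × 50 = 35.5, so X must be 31 to 35.
- Follow-up 66-74%: 0.66 × 50 = 33 and 0.74 × 50 = 37, so X must be 33 to 37.

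| Criterion | Highest P(in band) over all p | At true 80% |
|---|---|---|
| Outreach, P(31 ≤ X ≤ 35) | 0.544 (p = 0.661) | 0.060 |
| Follow-up, P(33 ≤ X ≤ 37) | 0.559 (p = 0.701) | 0.180 |

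The enrolment range, 30-44%, is measured on invitations, and the plan gives no number invited. If 50 enrolled were 30-44% of those invited (assumption: 50/0.44 = 114 to 50/0.30 = 167), that band could be met up to 88-93% of the time. The 54-56% figures do not extend to it.

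**3. The same ranges read as minimums.**

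| Criterion | True rate at the bound | Mid-range | Top of range |
|---|---|---|---|
| Outreach, P(X ≥ 31) | 0.562 (p = 0.62) | 0.796 (p = 0.665) | 0.937 (p = 0.71) |
| Follow-up, P(X ≥ 33) | 0.565 (p = 0.66) | 0.782 (p = 0.70) | 0.923 (p = 0.74) |

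**4. Precision that the sample can offer.** 95% Wilson intervals for illustrative results:

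| Result | Observed | Interval |
|---|---|---|
| 35 of 50 patients | 70% | 56-81% |
| 28 of 35 completers satisfied | 80% | 64-90% |
| 21 of 27 providers | 78% | 59-89% |
| 14 of 18 providers | 78% | 55-91% |

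The intervals are asymmetric, so a single ± figure would understate the uncertainty on the low side.

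**5. The f² = .08 part.** Section 7.2 names no test, f² scale or correlation. I tried three forms with m visits and N patients, all with error df (m−1)(N−1): an omnibus F test and a 1-df contrast, both with noncentrality .08 × (m−1)(N−1), and a repeated-measures F test with noncentrality .08 × N × m/(1−ρ), ρ = 0.5 assumed. Example for N = 50, m = 4: .08 × 3 × 49 = 11.76, giving omnibus power 0.82.

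| N | Visits | Omnibus | 1-df contrast | Repeated measures, ρ = 0.5 |
|---|---|---|---|---|
| 50 | 4 | 82% | 93% | >99% |
| 50 | 5 | 90% | 98% | >99% |
| 37 | 4 | 67% | 83% | 99% |
| 37 | 5 | 77% | 92% | >99% |
| 33 | 4 | 61% | 78% | 98% |
| 33 | 5 | 71% | 89% | 99% |

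The 33-37 completers are 66-74% of 50. Four visits match the baseline, 3-, 6- and 12-month analysis in Section 7. Five match the number of assessments in Section 9.7.2.

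**The case against.** The best defence is that the ranges were meant as minimums. Section 6.2 says only that results within the range would count as feasible, which does not say that a higher result fails. The companion rules, at least 75% of providers and at least 80% satisfied, are one-sided. This stands: the band is the strictest reading and probably not the intended one. What remains is that Section 7 never says that exceeding a range counts.

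A reader might set the 54-56% against the stated 80% and infer that the trial's power is really about 55%. The documents do not support that. One is a pass probability under one reading of a cut-off, and the other is a power claim with no hypothesis behind it. The outreach figure also assumes a single outcome per patient. Study 3 makes three attempts, and the plan does not say whether acceptance means the first, any or every one.

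A reader might also infer that the power for f² = .08 is false. It is not shown to be. At the 50 patients stated, every variant tried with four or five visits exceeds 80%. Lower values appear only if the sample is cut to completers, and the planned mixed models need not discard patients with partial data.

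Finally, this is a pilot, Section 7.2 says so, and no later decision is tied to passing the cut-offs. That limits the consequences. But a pilot need not claim power, and this one does.

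**Conclusion.** The point holds in two parts. First, the claim of more than 80% power for feasibility and acceptability has no basis as written, because neither has a hypothesis or a test. This is a gap in specification, not an arithmetic error, and rests on no assumption. Second, the patient feasibility rule is ambiguous, and the ambiguity is large. At a true 80% follow-up rate, the band reading is met 18% of the time, while the minimum reading is met over 99% of the time (P(X ≥ 33) = 0.994). These figures assume 50 patients in the denominator and one yes/no outcome each.

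The within-subjects power is under-specified but not contradicted: 82% to over 99% at N = 50, and 61% to over 99% at 33-37 completers, with four or five visits. The sample of 50 is not shown to be wrong for a pilot. How the 18-27 providers in Section 7.2 relate to the 200 staff in the synopsis is a separate clarification, since they may be different denominators. The two parts should be fixed, and doing so does not call the trial's validity into question.

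**What to change.** 1. In Section 7.2, delete the power claim for feasibility and acceptability and state the expected precision as 95% Wilson intervals, giving both limits, using the examples in the working.

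2. In Sections 6.2 and 7, restate the patient rule as observed rates at or above 30% (enrolment), 62% (outreach) and 66% (follow-up), so that exceeding a range counts as feasible. Report the interval beside each result.

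The cost is text only: no added patients, visits or data. The drawback is that a minimum rule with 50 patients still passes a true rate sitting exactly at the outreach or follow-up bound about 56-57% of the time. That is why the intervals should accompany it.
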